DIFFERENCE IN STRAIN ELASTOSONOGRAPGY BETWEEN BENIGN AND MALIGNANT PERIPHERAL PARENCHYMAL LUNG LESIONS

Document date: 16th November 2022

INTRODUCTION

Ultrasonography has been widely used for diagnosis since it was first introduced in clinical practice in the 1970s. For lung assessment, ultrasonography is not frequently used in medical practice.⁽¹⁾

Lung has long been thought to be an organ that cannot be examined by ultrasonography due to its high air content (>90%), which blocks the ultrasonic signal due to the large acoustic impedance differential between the superficial tissues of the chest.⁽²⁾

In recent years, the use of lung ultrasonography has expanded beyond emergency situations to include routine examinations of patients with chronic lung illnesses. Lung ultrasonography has several benefits, including cheap cost, real-time imaging, and the lack of radiation.⁽³⁾

Elastography was developed in the 1990s to map tissue stiffness and reproduce/replace the palpation performed by clinicians. Two main types of elastography are currently in use, strain elastography where the tissue displacement in response to gentle pressure is used to compute and image tissue

strain, and shear wave elastography where the speed of shear wave traversing tissue is measured and used to create an image of tissue stiffness.^(4, 5)

Elastosonography has been used to assess tissue stiffness and elasticity, particularly in liver, thyroid, breast, and prostate nodules suspected of cancer are currently investigable organs for non-invasive diagnostic imaging.^(6, 7)

The form, echogenicity, shadowing, and regularity of the margin are all factors to consider when assessing solid lesions with ultrasound. Thoracic ultrasound can also detect most of pleural pathologies e.g., effusion, pneumothorax, pneumonia, or bronchopneumonia consolidations in the subpleural zones, as well as local thickening (3 mm) of the pleural line.⁽⁸⁾

Lung ultrasound wave elastography (LUSWE) approach has the capability of assessing superficial lung tissue stiffness safely and swiftly with the objective of providing a noninvasive tool for evaluating lung elasticity.⁽⁹⁾

The lung surface includes the space between the parenchyma and intercostal muscles; the surface wave speed on the lung is contributed by both the lung and the muscle.⁽¹⁰⁾

Direct vibration stimulation on the lung surface is not achievable during lung testing. A vibration stimulation on the chest wall causes surface wave propagation on the lung.⁽¹¹⁾

An ultrasonic probe is used to detect the propagation of the tissue wave motion (usually a few micrometers). By indenting a medium and examining the

relationship between the indentation displacement and the generated force, the indentation technique may determine the elasticity of that medium.⁽¹²⁾

A local mechanical vibration on the chest safely generates the surface wave on the lung in LUSWE. Diagnostic ultrasonography is only utilized to identify the propagation of surface waves on the lung. Strain pictures are created by repeatedly applying modest pressure to the tissues using the transducers.^(13, 14)

Following tissue movement is tracked between pairs of echo frames, and strain is determined based on the axial gradient of the displacements. A stiff area endures less strain (deformation) than surrounding softer tissue when subjected to the same amount of force.^(9, 15)

Most hospitalized patients are not able to perform radiological imaging either due to unavailability or inability to ambulate the patients for imaging to be held. We suggested to perform bedside, relatively cheap and available, imaging modality to help in the differentiation between benign and malignant peripheral lung pathologies.

Lung elastography, to be used as diagnostic tool, is considered a new era worldwide; a new modality that will help to reduce the burden and the widespread use of chest computed tomography.⁽¹⁶⁾

AIM OF THE WORK

The aim of this study is to demonstrate the applicability and efficacy of strain elasto-sonographic measurements in differentiating between benign and malignant peripheral parenchymal lesions.

PATIENTS

This study will include patients recruited in cross-sectional sample till achieving requirement of 120 patients with benign and malignant subpleural parenchymal lesions.

Sample size was calculated by medical research institute and biomedical informatics, Medical Statistics Department, Alexandria University.

(APPENDIX A)

Patients enrolled in our study will be examined and investigated in chest department, in Alexandria Main University Hospitals.

Inclusion criteria:

- 1) Adult patients above age of 18 years old.
- 2) Patients with peripheral lung lesion.

Exclusion criteria:

- 1) Pure pleural lesions.
- 2) Clinical instability to reach the final diagnosis.
- 3) Inaccessibility by ultrasound.

METHODS

This is a diagnostic accuracy study with comparison to gold standard tests e.g., chest computed tomography, transthoracic biopsy, or microbiological analysis. All patients included in this study will give informed consent according to the guidelines of ethics committee, Alexandria Faculty of Medicine. (<http://www.med.alexu.edu.eg/wp-content/uploads/2012/04/Checklist-FINAL-20141.pdf>)

Informed consent is available at (<http://med.alexu.edu.eg/alexuniv/wp-content/uploads/2021/09/Standard-Operating-Procedure-2020-ethics.pdf>).

All patients will be subjected to:

- 1) Thorough history taking.
- 2) Complete physical examination.
- 3) CT scan chest.
- 4) Routine laboratory investigation profile.
- 5) Conventional methods to reach final diagnosis such as microbiological analysis, CT scan, fiberoptic bronchoscopy, and image guided biopsies.
- 6) Strain elastography done by superficial and deep probes, in which B mode is compared with the elastography image for real time assessment; strain ratio is obtained. Strain ratio between benign and malignant peripheral lung lesions to be evaluated.

Data collected from our research aim to estimate a cut-off value by which benign and malignant peripheral parenchymal lesions to be easily discriminated by ultrasonographic elastography.

Statistical methods:

Considering nominal data e.g., clinical features, CT findings, epidemiology, smoking status, and final diagnosis will be statistically analyzed using median, mode, MANN-WHITNEY, and Chi square tests.

While numerical data analysis as arithmetic mean is helpful in situation of age statistical distribution. Strain ratio interpretation, the telltale sign of our study, is directed towards comparison of the cut off value achieved with the final diagnosis of the patients.

Receiver operator characteristic (ROC) curve will be plotted to evaluate and assess the sensitivity and specificity of strain ratio obtained from elastography compared to final diagnosis for 60 of our patients from the total 120 patients recruited in the study.

While according to the remaining 60 patients, a multivariate Cox proportional hazard analysis would be held to validate and evaluate results obtained from the former 60 examined patients.

At the end of the study, sensitivity, specificity, area under the curve (AUC), accuracy of a certain cut-off value, positive predicted value (PPV) and negative predicted value (NPV) would describe the performance of strain ratio as a diagnostic tool in the main aim of the research.

ETHICS OF RESEARCH

Research on human or human products:

- Prospective study: Informed consent will be taken from patients. In case of incompetent patients, the informed consent will be taken from the guardians.
- Retrospective study: Confidentiality of records will be considered
- DNA / genomic material: Informed consent for DNA / genomic test and research will be taken from patients. No further tests will be carried out except with further approval of committee and patients. If the samples will travel outside Egypt, the researcher will be responsible for transportation and security approval.
- All drugs used in the research are approved by the Egyptian Ministry of Health

Research on animal:

- The animal species are appropriate for the test.
- After test, if the animal will suffer, it will be euthanized and properly disposed.
- After operation, it will have a proper postoperative care.

سأقوم بتسلیم الموافقات المبنیة على علم المريض الخاصة بالدراسة عند الانتهاء منها او عند طلبها
من اللجنة

RESULTS

The results obtained from this study will be tabulated and statistically analyzed using appropriate statistical methods and appropriate figures and diagrams.

DISCUSSION

The results obtained from this study will be discussed in the view of achievement of the aim and will be compared with any of the available published data in the same field of the research.

REFERENCES

1. Beach KW. 1975-2000: a quarter century of ultrasound technology. *Ultrasound Med Biol*. 1992;18(4):377-88.
2. Volpicelli G. Lung sonography. *J Ultrasound Med*. 2013;32(1):165-71.

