APPENDIX A

Alexandria University
Medical Research Institute
Biomedical Informatics &
Medical Statistics Department

Name: [name]

Sample Size Calculation

The main aim of this study is to demonstrate accuracy of elastosonographic measurements in differentiating benign vs malignant subpleural parenchymal lesions compared to clinical, radiological (CT/PET). A recent study concluded that the ROC curve elaborated for the diagnosis of malignancy by strain elastography showed an AUC of 0.688. ⁽¹⁾ Consequently, patients will be recruited in a cross-sectional sample till achieving the minimum required sample of 60 patients with benign vs 60 patients with malignant subpleural parenchymal lesions with 80% power.

Sample size was calculated using a two-sided, ROC curve test at .05 significance level using R software.

Program Citation:

R Core Team (2017). R: A language and environment for statistical computing. R Foundation for Statistical Computing, Vienna, Austria. URL <https://www.R-project.org/>.

Reference:

Calculated and reported by: [name] [name]
Assistant Professor of Medical Statistics, systematic reviews and Evidence Synthesis. Medical Statistics Department, Medical Research Institute-Alexandria University
Email: [contact]. LinkedIn: [name].
[contact]

[name] [name]
IMAS
26/3/2022

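### With no single final-diagnosis rule and no later check of benign labels, a cancer with coexisting infection can be counted as benign, biasing NPV upward and PPV downward

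*Combined protocol and SAP*

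**What the plan says.** The reference standard is described in three places, each time differently.

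- **Methods, design sentence:** "This is a diagnostic accuracy study with comparison to gold standard tests e.g., chest computed tomography, transthoracic biopsy, or microbiological analysis". The list is of examples, and its members are joined by *or*.
- **Methods, item 5 of the procedures for all patients:** "Conventional methods to reach final diagnosis such as microbiological analysis, CT scan, fiberoptic bronchoscopy, and image guided biopsies". This is an open list, which adds bronchoscopy. Item 3 separately requires a chest CT in every patient.
- **Appendix A:** the comparator is clinical and radiological (CT/PET). Microbiology and biopsy are not mentioned.

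Under Statistical methods, the strain ratio is judged against the final diagnosis, a term that is never defined. The planned measures are sensitivity, specificity, AUC and accuracy, and "positive predicted value (PPV) and negative predicted value (NPV) would describe the performance of strain ratio as a diagnostic tool".

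The Patients section describes "patients recruited in cross-sectional sample till achieving requirement of 120 patients". It excludes patients for "Clinical instability to reach the final diagnosis". No section mentions follow-up, repeat imaging or resolution of the lesion.

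**The concern.** Every planned accuracy measure depends on the benign or malignant label. A positive culture shows that infection is present. It does not show that a tumour is absent, since a peripheral tumour can have pneumonia behind it or be infected itself. The wording allows such a result to settle the label and provides no step at which the error would come to light. A rule that asked for more than CT would not close this gap, because a positive culture would satisfy it.

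NPV is where the error is least safe. The Introduction proposes the test for bedside use in patients who cannot readily be imaged, and hopes it will reduce the use of chest CT. In that setting a negative strain result could stand in for further work-up. A cancer that is labelled benign and is test-negative is scored as a true negative, although it is a missed cancer. A wrong label cannot be recovered at the analysis stage.

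**Working it through.** **Inputs from the documents.** 60 benign and 60 malignant patients, and AUC 0.688 (both Appendix A). The plan gives no expected NPV and no rate of wrong labels, so there is no planned figure to reproduce on this point.

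**Assumptions.** Of the 60 patients labelled benign, k are truly malignant; k = 3, 6 or 12 (5%, 10%, 20%). Malignant labels are correct. Except in step 4, the strain result is independent of the label error. Sensitivity s and specificity c are both 0.636, the Youden point of an equal-variance binormal curve with AUC 0.688: √2 × Φ⁻¹(0.688) = 0.693, and Φ(0.693/2) = 0.636.

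**1. Formulas.** True malignant = 60 + k; true benign = 60 − k.

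- Test-negatives: N = (60 + k)(1 − s) + (60 − k)c
- True NPV = (60 − k)c / N
- Reported NPV = [(60 − k)c + k(1 − s)] / N
- NPV bias = k(1 − s) / N, which is never negative
- Test-positives: P = (60 + k)s + (60 − k)(1 − c)
- True PPV = (60 + k)s / P; reported PPV = 60s / P
- Reported specificity = [(60 − k)c + k(1 − s)] / 60
- Reported AUC = (1 − k/60) × 0.688 + (k/60) × 0.5

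**2. k = 6.** True negatives 54 × 0.636 = 34.32. False negatives 66 × 0.364 = 24.05. N = 58.37. Mislabelled test-negatives 6 × 0.364 = 2.19. True NPV = 34.32/58.37 = 0.588; reported NPV = 36.51/58.37 = 0.625. (Products and differences use unrounded values.)

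| k | True NPV | Reported NPV | NPV bias (points) | True PPV | Reported PPV | Reported specificity (true 0.636) | Reported AUC (true 0.688) |
|---|---|---|---|---|---|---|---|
| 3 | 0.612 | 0.631 | +1.8 | 0.658 | 0.627 | 0.622 | 0.679 |
| 6 | 0.588 | 0.625 | +3.7 | 0.681 | 0.619 | 0.608 | 0.669 |
| 12 | 0.538 | 0.615 | +7.7 | 0.723 | 0.603 | 0.581 | 0.650 |

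**3. Other operating points, k = 6.**

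- s = c = 0.70: true NPV 37.8/57.6 = 65.6%, reported 39.6/57.6 = 68.8%, bias +3.1 points. This point is slightly better than AUC 0.688 allows, since a concave curve through it has AUC of at least 0.70.
- s = 0.80, c = 0.60: bias 1.2/45.6 = +2.6 points.
- s = 0.90, c = 0.80: bias 0.6/49.8 = +1.2 points.

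**4. Independence dropped, k = 6, s = c = 0.636 in the correctly labelled patients.**

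- All six mislabelled cancers test-positive: true and reported NPV are both 0.611, bias 0. Reported specificity is 34.32/60 = 0.572.
- All six test-negative: true NPV = 34.32/(34.32 + 21.87 + 6) = 0.552; reported NPV = 40.32/62.19 = 0.648; bias +9.6 points. Reported specificity rises to 40.32/60 = 0.672, and PPV is unaffected because no mislabelled cancer is test-positive.

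**5. ROC subset.** Statistical methods plots the ROC curve on 60 of the 120 patients. If these split evenly (an assumption), about 30 are benign and three wrong labels make 10%. The expected biases are then the same as for k = 6 in 60.

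**The case against.** The strongest reply is that the plan does not say what a critical reader may take from it. Four stronger readings are tempting, and the documents do not support them.

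- *A positive culture alone is sufficient proof.* The design sentence gives examples, not a decision rule. Every patient also has history, examination, laboratory tests and CT, and the strain ratio is compared with a final diagnosis, not with a culture. Reliance on microbiology alone is permitted, not stated.
- *The label is fixed at one time point.* The term cross-sectional describes recruitment. The exclusion tied to reaching a diagnosis implies that a work-up is expected. What can be said is that no later check is planned.
- *A non-specific biopsy is taken as benign.* No section says how such a result is classified.
- *NPV is overstated without qualification.* It is overstated only against the truth in the same patients. A correctly labelled 60:60 sample would give NPV 0.636 at the main operating point, above the 0.625 reported at k = 6; at 70%/70% it would give 42/60 = 70.0%, above 68.8%. The mislabelled sample contains more cancer (66 of 120, or 55%), and that is why its true NPV is lower still.

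It is also fair to say that the error rate is assumed and that infected cancers may not share the strain-ratio distribution of other cancers.

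These points limit the wording and the size of the claim. They do not remove the gap. CT in every patient does not close it, because no rule says how CT is weighed against a culture. The exclusion criterion removes patients who cannot be diagnosed; it does not verify those who are labelled benign.

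**Conclusion.** The concern holds in a limited form. The plan has no single final-diagnosis rule, its Methods and Appendix A name different comparators, and it plans no check of benign labels. A cancer with coexisting infection can therefore enter the benign group. How often this would happen cannot be known from the documents.

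The direction for NPV and PPV is certain against the truth in the same patients, if the only label error is cancers called benign: reported NPV is never too low and reported PPV never too high. Specificity and AUC usually fall, but specificity can rise if the mislabelled cancers are mainly test-negative.

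The size rests on assumptions. With 10% of 60 benign labels wrong and independence, the NPV bias is about +3 to +4 points at operating points near AUC 0.688, and smaller if the test is better (+1.2 at 90%/80%). Without independence it runs from 0 to about +10. This should be corrected before the labels are assigned.

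**What to change.** 1. Reconcile the Methods and Appendix A into one final-diagnosis rule for the analysis, stating which result settles the label when tests disagree.
2. Count a lesion as confirmed benign only with a specific benign histology, or with positive microbiology or a non-specific biopsy plus documented resolution or stability in routine records after a minimum interval fixed before the analysis.
3. Do not treat absence of records as confirmation, since a patient who never returned would otherwise pass. Class these patients as *benign, unconfirmed*.
4. Report AUC, sensitivity, specificity, PPV and NPV with and without the unconfirmed patients.

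This is a labelling rule for the analysis. It uses routine records, adds no procedure and changes no patient's management. The cost is the work of reviewing about 60 charts, later final labels, and a smaller confirmed benign group in the sensitivity analysis. Late recruits will more often be unconfirmed because less time will have passed.

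### The plan sets neither timing nor masking between the strain ratio and the final diagnosis, so review bias towards agreement cannot be excluded.

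*Combined protocol and SAP*

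**What the plan says.** The METHODS section of the combined protocol and SAP defines the design: "This is a diagnostic accuracy study with comparison to gold standard tests e.g., chest computed tomography, transthoracic biopsy, or microbiological analysis". It then lists what every patient undergoes. Item 3 is a chest CT. Item 5 is the diagnostic work-up: "Conventional methods to reach final diagnosis such as microbiological analysis, CT scan, fiberoptic bronchoscopy, and image guided biopsies". Item 6 is strain elastography, in which "B mode is compared with the elastography image for real time assessment; strain ratio is obtained". The INTRODUCTION describes how strain images arise in general: "Strain pictures are created by repeatedly applying modest pressure to the tissues using the transducers".

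Statistical methods plans a ROC curve for the "sensitivity and specificity of strain ratio obtained from elastography compared to final diagnosis for 60 of our patients", with the other 60 used for validation. No cut-off is fixed in advance: "Data collected from our research aim to estimate a cut-off value by which benign and malignant peripheral parenchymal lesions to be easily discriminated". The results to be reported include "sensitivity, specificity, area under the curve (AUC), accuracy of a certain cut-off value", together with PPV and NPV.

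Four things are stated nowhere in METHODS, Statistical methods or Appendix A:

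- who performs or reads the elastography;
- what that person knows of the CT, biopsy or microbiology;
- when the scan takes place relative to the diagnosis;
- whether those who assign the diagnosis have seen the strain ratio.

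**The concern.** Every planned result measures agreement between the strain ratio and the final diagnosis. If either is obtained with knowledge of the other, agreement can be created by the process rather than by the lesion. Two routes are open:

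- **Diagnosis to ratio.** The ratio is obtained live, and no rule is given for the region of interest, the reference tissue or repeat measurements. A person who knows the lesion is malignant has room to settle on a frame or region that fits.
- **Ratio to diagnosis.** The reference standard is an open list that includes CT. Where the diagnosis rests on judgement, a known ratio can influence it.

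Both routes push towards agreement. A cut-off derived from such data would carry the bias with it. The second 60 patients offer no protection, because their ratios and diagnoses are obtained in the same way. The INTRODUCTION presents the method as a bedside aid for patients who cannot easily be imaged. Accuracy obtained with the diagnosis in hand would not answer that question. Nor can it be repaired later, because a live measurement taken unmasked cannot be taken again masked once the diagnosis is known.

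**Working it through.** **Step 1. The text.** Three safeguards were looked for in each relevant section.

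| Safeguard | METHODS items 1–6 | Statistical methods | Appendix A |
|---|---|---|---|
| Ratio recorded before diagnosis known | not stated | not stated | not stated |
| Operator or reader unaware of results | not stated | not stated | not stated |
| Diagnosis assigned without the ratio | not stated | not stated | not stated |

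The items are introduced only as things all patients undergo. The numbering is not stated to be a time order.

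**Step 2. Inputs for an illustration of size.** From Appendix A: planning AUC ("showed an AUC of 0.688"), 60 benign vs 60 malignant, two-sided 0.05, 80% power. From Statistical methods: the ROC is drawn in 60 of the 120. Assumed here: null AUC 0.5 (not stated), normal ratios with equal variance, a 30/30 split of the ROC subset, and a shift b, in SD units, by which knowledge of the diagnosis widens the gap between benign and malignant. The documents give no value for b.

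**Step 3. The plan's own figure.** With Hanley–McNeil variances, a two-sided 0.05 test of AUC 0.688 against 0.5 reaches 80% power at 36 per group; 60 per group gives about 96%. The stated 60 per group at 80% power is therefore not reproduced under a null of 0.5. That is a separate matter and depends on the unstated null. The 60 per group is taken as given below.

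**Step 4. Effect on a test with true AUC 0.688.** Separation d = √2 × Φ⁻¹(0.688) = 1.4142 × 0.4902 = 0.693 SD. Apparent AUC = Φ((d + b)/√2). Balanced sensitivity = specificity = Φ((d + b)/2).

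| b (SD) | (d + b)/√2 | AUC | Sens = spec |
|---|---|---|---|
| 0 | 0.490 | 0.688 | 0.636 |
| 0.1 | 0.561 | 0.713 | 0.654 |
| 0.2 | 0.632 | 0.736 | 0.672 |
| 0.3 | 0.702 | 0.759 | 0.690 |

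**Step 5. Effect on a test with true AUC 0.5.** Apparent AUC = A = Φ(b/√2). The probability of declaring it better than chance is Φ((A − 0.5 − 1.96 × SE₀)/SE_A), where SE₀ and SE_A are the Hanley–McNeil standard errors at 0.5 and at A. SE₀ is 0.0529 at 60 vs 60 and 0.0752 at 30 vs 30.

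| b (SD) | A | 60 vs 60 | 30 vs 30 |
|---|---|---|---|
| 0 | 0.500 | 2.5% | 2.5% |
| 0.1 | 0.528 | 8% | 6% |
| 0.2 | 0.556 | 18% | 11% |
| 0.3 | 0.584 | 35% | 20% |

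Worked case, b = 0.2 at 60 vs 60: (0.5562 − 0.5 − 1.96 × 0.0529)/0.0525 = −0.904, and Φ(−0.904) = 0.18.

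**The case against.** The strongest reply is that silence is not an effect.

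- **Order of tests.** A reader might infer from elastography standing last in the list that the diagnosis is already known at scanning. The documents do not support that: the list is a checklist with no stated sequence. This stands. The gap is a missing safeguard, not a demonstrated breach.
- **Operator influence.** A reader might take it as fact that this study's operator compresses by hand and can steer the ratio. The sentence on transducer pressure is general background, next to text on a vibration technique, and item 6 names no compression method. The INTRODUCTION also describes strain as computed from tracked displacement, so the ratio is not a purely subjective score. Operator influence is a reasonable inference, but how far knowledge of the diagnosis could move the ratio is unknown.
- **Choice of sample.** The 60 vs 60 figures give the larger false-positive rates, while Statistical methods puts only 60 patients in the ROC. This stands, which is why both cases are shown.
- **CT.** A lock placed before histology, bronchoscopy and microbiology does nothing where CT alone settles the diagnosis, and hiding the CT from the operator may need another person to read it. This also stands and limits what the fix can achieve.

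None of these points supplies the missing condition on timing or masking.

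**Conclusion.** The point holds as a gap in the design. The plan leaves the strain ratio and the final diagnosis free to inform each other, so review bias towards agreement cannot be excluded, and the validation half could not reveal it. It is more than missing detail, because the study's whole output is that agreement and the problem cannot be corrected after data collection.

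A reader might go further and conclude that the AUC will be too high, or too high by a given amount. The documents do not support that. Inflation occurs only if the diagnosis or the ratio was in fact known and had an influence. The figures above show what assumed shifts of 0.1 to 0.3 SD would do under an equal-variance binormal model with a null AUC of 0.5. They do not estimate the bias in this study.

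**What to change.** In METHODS item 6, state that the strain ratio and its stored image are recorded, time-stamped and locked before any histology, bronchoscopy or microbiology result is available. In item 5, state that the final diagnosis is assigned without access to the ratio. In Statistical methods, flag every patient whose diagnosis was already known at scanning, including those settled on CT alone, and repeat the ROC without them as a sensitivity analysis.

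The cost is protocol wording, a date/time field on the scan form, some scheduling, and a smaller sample in the sensitivity analysis. The planned sample size does not change, and no extra reader or procedure is needed. Some bias may remain because the operator may have seen the CT. Giving the operator only the lesion's location would reduce it, but that may need someone else to read the CT, so it is best left optional where existing staff allow it.

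### The ROC analysis uses 60 of the 120 patients and the other 60 yield no accuracy estimate; using all 120 with bootstrap optimism correction is the better plan

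*Combined protocol and SAP*

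**What the plan says.** Four places in the combined protocol and SAP bear on this.

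- **Methods:** the cut-off is to be found from the study's own data: "Data collected from our research aim to estimate a cut-off value". No selection rule is given.
- **Statistical methods, ROC paragraph:** sensitivity and specificity of the strain ratio are assessed "compared to final diagnosis for 60 of our patients from the total 120 patients recruited in the study". For the remaining 60, "a multivariate Cox proportional hazard analysis would be held to validate and evaluate results obtained from the former 60 examined patients". The document does not say how the two sets of 60 are formed. It does not exchange their roles and plans no cross-validation, bootstrap or other optimism correction.
- **Statistical methods, closing paragraph:** sensitivity, specificity, AUC, "accuracy of a certain cut-off value, positive predicted value (PPV) and negative predicted value (NPV) would describe the performance of strain ratio". No analysis set is named.
- **Appendix A:** the ROC test is sized on "60 patients with benign vs 60 patients with malignant subpleural parenchymal lesions with 80% power", after citing an earlier study whose ROC curve "showed an AUC of 0.688". That is the full sample of 120 given in the Patients section.

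**The concern.** The study's product is one cut-off and a statement of how well it performs. A cut-off chosen to look best in a set of patients looks better there than it will in new patients, so accuracy needs either separate patients or a correction. The plan shows awareness of this by reserving 60 patients, but the analysis assigned to them cannot do the job. A Cox model needs follow-up time and events, which a cross-sectional study does not have, and it produces hazard ratios, not sensitivity or specificity.

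Replacing the Cox model with a proper test of the locked cut-off would remove the bias, but would still leave the cut-off resting on one half of the patients and its accuracy on the other. At stake are the bias and precision of the published accuracy figures, and agreement between the ROC analysis and the sample size that justifies it.

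**Working it through.** **Inputs.** From Appendix A: AUC 0.688, two-sided 0.05, 80% power, 60 per group. From Statistical methods: ROC on 60, other use of 60. Assumed, because the document does not give them: null AUC 0.5, 30 benign and 30 malignant in each half, an equal-variance binormal marker, and a cut-off at the maximum Youden index (sensitivity + specificity − 1).

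**1. The plan's own figure.** Across the variance formulas tried, 80% power against a null AUC of 0.5 needs 32 to 37 patients per group, so the stated 60 per group is not reproduced. A null of about 0.54 to 0.55 would give roughly 80% power with 60 per group, but no null is stated.

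**2. The ROC test on half the sample.** The Hanley-McNeil variance with n per group is

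Var = [A(1−A) + (n−1)(Q1−A²) + (n−1)(Q2−A²)] / n², with Q1 = A/(2−A) and Q2 = 2A²/(1+A).

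At A = 0.688: Q1 = 0.5244, Q2 = 0.5608, A² = 0.4733, A(1−A) = 0.2147.

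- n = 30: SE = √(4.232/900) = 0.0686; null SE = √(5.083/900) = 0.0752. Power = Φ[(0.188 − 1.96×0.0752)/0.0686] = Φ(0.59) = 72%. 95% half-width = 1.96×0.0686 = 0.134.
- n = 60: SE = √(8.388/3600) = 0.0483; null SE = √(10.083/3600) = 0.0529. Power = Φ[(0.188 − 1.96×0.0529)/0.0483] = Φ(1.75) = 96%. 95% half-width = 0.095.

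Other variance formulas give 72% to 78% for 30/30, all below 80%. With a 20/40 or 40/20 mix it is 66% to 68%. For a sensitivity of 0.70, the half-width is 1.96√(0.70×0.30/30) = 0.164 on 30 malignant patients and 0.116 on 60.

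**3. Bias and precision at a data-chosen cut-off.** The AUC of 0.688 corresponds to a mean difference of √2·Φ⁻¹(0.688) = 0.693 SD. Simulated studies (1,000 or more per run) compared four ways of reporting the Youden index with its true value at the chosen cut-off:

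| Reported estimate | Bias | RMSE |
|---|---|---|
| Same 60 that set the cut-off, uncorrected | about +0.13 | about 0.16 |
| Locked cut-off tested on the other 60 | about 0 | 0.118 |
| All 120, uncorrected | about +0.09 | 0.112 |
| All 120, bootstrap optimism correction | about +0.03 | 0.084 |

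The first row is the plan read literally. The true value is about 0.246, so it would report on average about 0.246 + 0.13 = 0.38.

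For sensitivity, the RMSE is about 8.5 points with the locked hold-out and 6.0 with all 120 corrected. On the Youden index, (0.118/0.084)² = 1.97, so the hold-out's mean squared error is about twice as large, even with the residual bootstrap bias counted. The ordering holds at other AUCs: 0.116 versus 0.084 at 0.75, and 0.105 versus 0.078 at 0.85.

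**4. The cut-off itself.** Its SD falls from about 0.47–0.48 to 0.38–0.40 marker SDs when all 120 are used. Its true Youden index rises only from 0.246 to 0.253, because performance is flat near the optimum.

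**The case against.** **A hold-out is a legitimate design.** With a locked cut-off it is unbiased, and a Wilson interval on it covers at 95%. The bootstrap correction leaves about 1.5 points of optimism in each of sensitivity and specificity, or 0.03 on a true Youden index near 0.25. Repeated 10-fold cross-validation has almost no bias and improves the Youden-index error (0.096 versus 0.119), but does not reduce the separate errors of sensitivity and specificity. This stands: for those two measures the gain in precision is bought with a small bias. The RMSE counts that bias and still favours using all 120.

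**The hold-out comparison does not price the written plan.** This also stands. A reader might infer that 8.5 versus 6.0 points describes the figures this study will publish. It does not, because the document plans no hold-out accuracy estimate. The literal plan is the uncorrected row of the table, which is worse.

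**The published figures may not rest on half the data.** The closing paragraph names no subset, and the two sets of 60 may be a slip for the 60 benign and 60 malignant of Appendix A. A reader might infer that half the patients are certainly wasted; the documents do not settle that. Uncorrected pooling of all 120 would still overstate the Youden index by about 0.09, so a correction is needed on either reading.

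**The second 60 might be a check over time.** The wording "to validate and evaluate results obtained from the former 60 examined patients" could mean order of examination. Strain imaging depends on pressure applied by hand, so drift in technique is conceivable, and a pooled bootstrap cannot detect it. It is therefore too strong to say that a hold-out could serve only to remove optimism. But no chronological split is stated, and the Cox model would not provide that check.

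**Conclusion.** The point holds as a matter of bias in the plan as written, and of efficiency in its natural repair. As written, the one explicit accuracy estimate is uncorrected and comes from the patients who set the cut-off (Youden index too high by about 0.13, RMSE about 0.16). The ROC test is run on half the sample that Appendix A assigns to it, with power of about 72% to 78% against an assumed null of 0.5, compared with about 96% on all 120. If the second half were repaired into a locked-cut-off test, it would be valid but imprecise, with about twice the mean squared error of the Youden index.

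A reader might also infer that the split produces a materially worse cut-off. The figures do not support that: the true Youden index differs by 0.007.

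The sizes rest on the binormal model, the Youden rule and a 30/30 mix, none of which the document states. The change should be made, but nothing here invalidates the data to be collected.

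**What to change.** First reconcile the ROC paragraph, the closing paragraph of Statistical methods and Appendix A, and name one analysis set for every accuracy measure. Then replace the two-halves text with wording such as:

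> *The ROC curve and the cut-off, chosen by a prespecified rule (for example the maximum Youden index), will be estimated on all 120 patients. Sensitivity, specificity and accuracy at the cut-off will be corrected for optimism by bootstrap resampling within diagnosis group (at least 500 samples), repeating the cut-off rule in each sample. Apparent and corrected values will both be reported, with 95% confidence intervals by a named method (for example Wilson intervals around the corrected values). This is internal validation; external or temporal validation remains to be done.*

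The interval method must be named because the choice matters. In simulation at AUC 0.688, a Wilson interval around the corrected sensitivity was 0.22 wide with 94% coverage. A percentile bootstrap interval shifted by the optimism was 0.47 wide, against 0.30 for the hold-out's Wilson interval.

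The cost is plan wording and a short R script, with no extra patients or procedures. The downsides are the residual optimism noted above, which should be disclosed, and the loss of a separate hold-out. If the sponsor intended the second 60 as a chronological check, the plan should say so and describe it as a test of the locked cut-off reporting sensitivity and specificity, accepting the lower precision.
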